Subjects who discontinue treatment due to lack of efficacy or to an AE prior to 12 weeks following achievement of a platelet count of at least 50,000/ μ L, will be considered failures. The null and alternative hypotheses for the comparison of fostamatinib vs. placebo are as follows:

$$H_0: p_F = p_P \quad \text{vs.} \quad H_1: p_F \neq p_P$$

where p_F and p_P denote the true proportions achieving and maintaining a stable platelet count for fostamatinib and placebo, respectively. The null hypothesis will be tested using a 2-sided

McNemar's test conducted with a significance level of 0.05. This analysis will be performed for the Treated and Per Protocol populations.

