## 2.0 STUDY OBJECTIVES

The primary objective of this study is to assess the long-term safety of fostamatinib in subjects with persistent/chronic ITP.

The secondary objectives of this study are:

[figure not shown]
- To establish the long-term efficacy of fostamatinib in achieving and maintaining a stable platelet count in subjects who complete the treatment phase of Study C-935788-047 or Study C-935788-048
- To assess the pharmacokinetic (PK) profile of fostamatinib in subjects with persistent/chronic ITP.

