## 3.0 INVESTIGATIONAL PLAN

### 3.1 Overall Study Design Summary

This is a Phase 3 multi-center, open label extension study to evaluate the long-term safety and efficacy of fostamatinib in achieving and maintaining a stable platelet response in subjects with persistent/chronic Immune Thrombocytopenic Purpura (ITP). For the purpose of this study, the term ‘subject’ will refer to patients with persistent/chronic ITP participating in this study. Up to 150 subjects will be enrolled at multiple sites. The study will consist of monthly visits for 18 months followed by every-other-month visits for a maximum of 5 years of treatment or until commercial availability of drug, whichever comes first.

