### 3.4. Determination of Sample Size

No sample size calculations were performed for this study. The sample size will be based upon the number of patients in the C-935788-047 and C-935788-048 studies who are eligible to participate in this study and choose to participate.

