### 3.5. Changes to the Protocol-Specified Analyses

For the method of assigning subject to treatment (as mentioned in Section 3.2), protocol states that the responders will initiate open-label fostamatinib treatment with the dose and regimen that was efficacious in achieving a stable platelet response in Study C-935788-047 or C-935788-048. In reality, the patients were not required to be stable responders but rather to have at least one platelet count of at least 50,000/ $\mu$ L.

The protocol defines the baseline value as the last measurement for the corresponding variable prior to the first randomized dose at Visit 3 in Study C-935788-047 or C-935788-048. For the analyses described by this SAP, the baseline value will be defined as the last measurement for the corresponding variable prior to the first dose of fostamatinib in Study C-935788-047 or C-935788-048 (for fostamatinib patients in the previous study) or the present study (for placebo patients in the previous study), unless specified otherwise in the SAP.

For secondary efficacy endpoint, duration of stable platelet response, has been changed to duration of platelet response, the protocol specified that subjects who drop out of the study before achieving a platelet response will be assigned duration of platelet response of 0 and will be censored. In addition to the duration of platelet response, total duration of platelet response is also defined in **Section 4.4** in this SAP and will be analyzed.

For secondary efficacy endpoint, subjects with reduction in the dose of concomitant ITP therapy while maintaining an adequate platelet count (yes/no), the protocol states that a two-sided, McNemar's test was to be performed to compare the proportions of subjects achieving a reduction in the dose of concomitant ITP therapy while maintaining an adequate platelet count between the fostamatinib and placebo treatments. In this SAP, no McNemar's test will be performed, instead the patient level of listing for the concomitant ITP therapy using during the present study will be provided in data listing.

Also, per protocol version 5, one-sample t-test was to be used to evaluate the mean change from baseline for each post-baseline time point for the safety endpoints of systolic and diastolic blood

pressure, liver function test [i.e., ALT, AST, alkaline phosphatase, and bilirubin (total, direct, and indirect)] and ANC. This one-sample t-test will not be performed.

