## 10.0 EFFICACY ANALYSES

### 10.1 Primary Efficacy Endpoint

#### 10.1.1 Version 1

The first version of the primary efficacy endpoint is defined in **Section 4.4** and applies for all patients entering C-935788-049 study. It will be summarized using counts and percentages, together with a 95% exact (Clopper-Pearson) confidence interval for the true percentage of Version 1 responders.

#### 10.1.2 Version 2

The second version of the primary efficacy endpoint is defined in **Section 4.4** and applies for all patients randomized to placebo in either C-935788-047 or C-935788-048 studies and entering C-935788-049 study.

These endpoints will be summarized based on a shift table (**Table 3** below) presenting shifts in responder status from placebo treatment in the C-935788-047 or C-935788-048 studies to fostamatinib treatment in the C-935788-049 study using counts and percentages, together with 95% exact (Clopper-Pearson) confidence intervals for the true percentage of Version 2 responders. In addition, the following hypothesis test will be conducted:

$H_0: P_{01} - P_{10} = 0$  vs.  $H_a: P_{01} - P_{10} \neq 0$ ,

Where  $P_{01}$  denotes true proportions of non-responders from placebo patients in C-935788-047 or C-935788-048 studies who become Version 2 responders in C-935788-049 study and

$P_{10}$  denotes true proportions of stable responders from placebo patients in C-935788-047 or C-935788-048 studies who become Version 2 non-responders in C-935788-049 study.

here  $P_{01}$  and  $P_{10}$  are estimated by  $\frac{c}{a+b+c+d}$  and  $\frac{b}{a+b+c+d}$ , respectively, where a, b, c and d are number of patients as defined in **Table 3** below

**Table 3.** Shift of Response Status For Version 2 Response

Placebo Patients in C-935788-047 or C-935788-048 Studies Who Entered C-935788-049 Study

		Version 2 Responders in C-935788-049 Study		
		Yes	No	Total
Stable Responder in C-935788-047 or C-935788-048 Studies	Yes	a	b	a+b
	No	c	d	c+d
	Total	a+c	b+d	a+b+c+d

The p-value of the null hypothesis test for  $H_0: P_{01} - P_{10} = 0$  will be calculated using a 2-sided exact McNemar's test with a significance level of 0.05. The 95% confidence intervals for the difference in proportion of  $P_{01} - P_{10}$  will be calculated using normal approximation method.

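### The Version 2 difference gets an unnamed normal-approximation interval beside an exact McNemar test; read as Wald, it usually covers less than 95% and can exclude zero at p = 0.125

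*SAP*

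**What the plan says.** SAP 10.1.2 covers patients who received placebo in study 047 or 048 and then entered study 049. It sets out a 2×2 shift table with b patients who were stable responders on placebo only, c who were Version 2 responders on fostamatinib only, and n = a + b + c + d. The p-value for H0: P01 − P10 = 0 "will be calculated using a 2-sided exact McNemar's test with a significance level of 0.05". The responder percentages get exact (Clopper-Pearson) "confidence intervals for the true percentage of Version 2 responders". The 95% interval for the difference itself, however, "will be calculated using normal approximation method", and nothing more is said about it.

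Protocol 10.4.1.2 asks for a two-sided "McNemar's test conducted with a significance level of 0.05", without the word exact and with no interval for the difference. On the concomitant-therapy endpoint, SAP 3.5 says: "In this SAP, no McNemar's test will be performed". Version 2 is therefore the only between-treatment hypothesis test left.

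On size, SAP 3.1 says "Up to 150 subjects will be enrolled at multiple sites" and SAP 3.4 says "No sample size calculations were performed for this study". SAP 2.0 makes long-term safety the primary objective.

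**The concern.** The section uses exact methods for the test and for the single proportions, then switches to a large-sample method for the effect estimate that readers will quote. Responders on placebo are likely to be few, so b may be zero or close to it, which is where a normal approximation for a paired difference is weakest. Three things can go wrong with the uncorrected form:

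- it covers less than its nominal 95%;
- it can exclude zero beside a non-significant p-value;
- it has zero width when there are no discordant pairs.

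The formula is also open. Two programmers following the same sentence could report intervals that fall on opposite sides of zero. Neither document says how to present an interval and a p-value that disagree.

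**Working it through.** The plan states no interval, power or sample size for Version 2, so there is no figure to reproduce.

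**Inputs.** From SAP 10.1.2: the estimators c/n and b/n, the exact two-sided test at 0.05, and the 95% level. From SAP 3.1: the cap of 150 subjects. Assumed, because the documents are silent: n = 40 to 50 (with n = 30 and 75 as a wider range), P01 = 0.05 to 0.30 in steps of 0.05, and P10 = 0, 0.02, 0.05 or 0.10. That makes 11 × 6 × 4 = 264 settings.

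**Formulas**

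- Exact p = min{1, 2·P(X ≤ min(b, c))}, with X ~ Bin(b + c, 0.5).
- Wald: d = (c − b)/n, SE = √[(b + c) − (c − b)²/n]/n, limits d ± 1.96·SE. The corrected form widens each side by 1/n.
- Bonett-Price: p01 = (c + 1)/(n + 2), p10 = (b + 1)/(n + 2), d = p01 − p10, SE = √[(p01 + p10 − d²)/(n + 2)].

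**One table: n = 45, b = 0, c = 4**

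- Exact p = 2 × 0.5⁴ = 0.125.
- Wald: d = 4/45 = 0.0889; SE = √(4 − 16/45)/45 = 0.0424; limits 0.6% to 17.2%. Zero is excluded.
- Wald with 1/n: 1/45 = 0.0222; limits −1.6% to 19.4%. Zero is included.
- Bonett-Price: p01 = 5/47, p10 = 1/47, d = 0.0851, SE = 0.0506; limits −1.4% to 18.4%. Zero is included.

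The Wald result does not hinge on n = 45. For b = 0, c = 4 the ratio d/SE is 2/√(1 − 4/n), which exceeds 1.96 at any n above 4. For n = 20 to 75 the reverse conflict (p ≤ 0.05 with zero inside the Wald interval) never occurs, so the error always favours a difference.

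**Operating characteristics**, by summing the trinomial probabilities over every (b, c), n = 40 to 50. Disagreement means that the interval excludes zero while exact p > 0.05.

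| P10 | Wald coverage | Wald disagreement | Bonett-Price coverage | Bonett-Price disagreement, at most |
|---|---|---|---|---|
| 0 | 86–95% | 0.1–38% | 93–100% | 18.5% |
| 0.02 | 86–95% | 2–27% | 94.9–99.7% | 13.7% |
| 0.05 | 93–95% | 4–20% | 95.2–98.8% | 10.3% |
| 0.10 | 93–95% | 5–14% | 95.2–98.8% | 9.2% |

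(The Bonett-Price coverage in the last two rows is one range for both.)

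- Settings below 95%: Wald 259 (median 93.8%, minimum 86.4%); Bonett-Price 27 (median 96.0%, minimum 93.0%); corrected Wald 24 (minimum 87%, at P10 = 0, P01 = 0.05).
- Disagreement of corrected Wald: none at P10 = 0, at most 0.8% at 0.02, at most 2.9% at 0.05 and 0.10.
- Wider range of n, Wald: n = 30, coverage 78–97%, disagreement 3–39%; n = 75, 89–95% and 0–35%.
- Wider range of n, Bonett-Price: n = 30, coverage 94.9–99.9%, disagreement 0.7–18.6%; n = 75, 93.9–98.0% and 0–7.2%.

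**No true difference.** At P01 = P10 = 0.10, zero is excluded by Wald in 7.0–7.2% of trials and by Bonett-Price in 3.8–4.0%; the exact test rejects in 1.9–2.2%. At P01 = P10 = 0.02, Wald excludes zero in only 0.8–1.4%, so under-coverage is usual but not universal.

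**Zero width.** The probability of no discordant pairs is (1 − P01 − P10)ⁿ. With P01 = 0.05 and P10 = 0 this is 0.95⁵⁰ = 8% to 0.95⁴⁰ = 13%; at P10 = 0.02 it is 3–5%.

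**The case against.** The strongest reply is that much of the conflict comes from the exact McNemar test, not from the interval. The test is conservative: with P01 = P10 = 0.05 it rejects in only 0.5–0.9% of trials. An exact unconditional interval with score ordering, which covered 95.3–99.7% at n = 40, 45 and 50, also excludes zero for n = 45, b = 0, c = 4 (about 0.15% to 21.2%) and disagrees with the test in up to 38% of trials. Disagreement alone therefore does not prove that the Wald interval is faulty. That stands; the defect properly attributed to the interval is under-coverage.

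The typical shortfall is also small, a little over one percentage point at the median. Only 20 of the 264 settings fall below 90%, all with P10 = 0 and P01 of 0.15 or less, or with P10 = 0.02 and P01 = 0.05. That stands too.

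A 1/n-corrected interval is also a normal approximation, and it nearly removes the disagreement. This is fair, but the SAP does not say it is intended, and the conclusion here is conditional on the uncorrected reading.

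Finally, the exact test already decides H0, the shift-table counts let a reader recompute the interval, and efficacy is secondary in this study. These points limit the importance of the concern but do not answer it.

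**Conclusion.** The concern holds as a low-priority improvement. The interval method is unspecified. Under its usual Wald reading, coverage falls short in nearly every setting examined, mostly by one or two points, and by up to about nine points when discordant pairs are very few. The interval can also point to a difference that the pre-specified test does not support. The test decision and its type I error do not change. What is at stake is the accuracy and consistency of one reported interval, for the only treatment comparison still tested. The numbers of placebo patients and the response rates behind these figures are assumptions; the pattern persists at n = 30 and n = 75.

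**What to change.** In SAP 10.1.2, replace the normal approximation with the Bonett-Price adjusted interval (add 1 to b and to c, and 2 to n), described as approximate, and say in words that the exact p-value decides H0.

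This does not bring full agreement with the test. At n = 45, b = 0, c = 5 (p = 0.0625) gives 0.03% to 21.2%, and b = 1, c = 7 (p = 0.070) gives 0.1% to 25.4%. If an interval that always agrees with the test is wanted as well, add the Clopper-Pearson interval for c/(b + c): for b = 0, c = 4 it runs from 39.8% to 100% and contains 50%. If guaranteed coverage matters more, name an exact unconditional interval and its ordering statistic, accepting that disagreement with the p-value remains.

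The cost is one or two sentences and a few lines of code. The protocol specifies no interval for this difference, so its text need not change. The price is a less favourable lower limit and some conservatism when discordant pairs are very few.

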## 10.2 Secondary Efficacy Endpoint

The secondary efficacy endpoints are as follows:

### 10.2.1 Duration of Platelet Response

Duration of platelet response is defined in **Section 4.4**. It will be analyzed using the Kaplan-Meier method, and the Kaplan-Meier estimate of the median duration of platelet response will be presented together with the 95% confidence interval for the true median. The descriptive summary for the duration of platelet response will also be presented with number (n) of patients with non-missing duration of platelet response and mean/ standard deviation (SD)/ 25th percentile/ median/ 75th percentile/ minimum/maximum of duration of platelet response.

In addition, the duration of platelet response will also be analyzed for the following subgroups of patients:

- C-935788-047 or C-935788-048 fostamatinib subjects who were C-935788-049 primary efficacy endpoint version 1 responders
- all C-935788-049 primary efficacy endpoint version 1 responders
- C-935788-047 or C-935788-048 placebo patients who were C-935788-049 primary efficacy endpoint version 2 responders.

The same analyses as mentioned above will be conducted for the duration of platelet response based on the additional definitions as mentioned in **Appendix 14.2**.

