7.3 Discontinuation of Nonresponders

After 3 months (12 weeks) of treatment, (and a minimum of 4 weeks treatment at 150 mg PO *bid*, unless this higher dose was not tolerated), any subject whose platelet count consistently

remains $< 50,000/\mu\text{L}$ should be discontinued from the study, unless tangible clinical benefit from the use of fostamatinib is evident and the Sponsor agrees (discuss any exceptions with the Sponsor's Medical Monitor). Examples of tangible clinical benefit may include, but are not limited to:

- Credible increase in platelet count (eg, increase in platelet count of at least $20,000/\mu\text{L}$ over the initial baseline to a count $\geq 30,000/\mu\text{L}$)
- Reduction in bleeding
- Reduction in the need for rescue therapy

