#### 4.4. Secondary Efficacy Endpoints

The secondary efficacy endpoints are as follows:

- The duration of platelet response (months) and total duration of platelet response (months)
- Patients with reduction in the dose of concomitant ITP therapy while maintaining an adequate platelet count (yes/no)

Duration of platelet response will be defined as the length of time from when the patient first achieves a platelet count of at least 50,000/ $\mu$ L until the first of two visits with platelet counts < 50,000/ $\mu$ L that are at least 4 weeks apart without an intervening visit with a platelet count  $\geq$  50,000/ $\mu$ L unrelated to rescue therapy.

Four additional definitions of duration of platelet responses are stated in **Appendix 14.2**

Patients who drop out of the study before achieving a platelet response (i.e., achieving a platelet count of  $\geq$  50,000/ $\mu$ L) will be assigned a value of 0 for this endpoint. Patients who drop out of the study by the time of database lock while still maintaining a platelet response will be censored as of the time of the last platelet measurement prior to dropping out of the study. Similarly, patients who remain in the study by the time of database lock while still maintaining a platelet response will be censored as of the time of the last platelet measurement prior to the time of database lock. For patients who have achieved and are maintaining a platelet response but who have discontinued treatment due to lack of efficacy or to an AE by the time of database lock, duration of platelet response will be defined as the time from first achieving a platelet count of  $\geq$  50,000/ $\mu$ L until discontinuation of treatment.

The total duration of platelet response is defined as the sum of all durations of platelet responses.

Regarding the secondary efficacy endpoint of patients with reduction in the dose of concomitant ITP therapy while maintaining an adequate platelet (yes/no), a patient is said to have reduction while maintaining an adequate platelet count if the date of reduction of dose of concomitant ITP therapy occurs within the span of the duration of a platelet response during the C-935788-049 study and the reduction was not prompted by AE.

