### 10.2.2 Total Duration of Platelet Response

The total duration of platelet response is defined in **Section 4.4** and will be analyzed in the similar way as duration of platelet response as mentioned in **Section 10.2.1**.

The same analyses as mentioned above will be conducted for the total duration of platelet response based on the additional definitions as mentioned in **Appendix 14.2**.

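### SAP 10.2.1 adds a plain summary of response durations with no rule for censored values: its mean is too short, and its median and quartiles are at or below the Kaplan-Meier ones

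*SAP*

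**What the plan says.** SAP 10.2.1 names Kaplan-Meier as the method: "the Kaplan-Meier estimate of the median duration of platelet response will be presented together with the 95% confidence interval for the true median". It then adds a second summary of the same variable: "The descriptive summary for the duration of platelet response will also be presented with number (n) of patients with non-missing duration of platelet response", followed by mean, SD, minimum, maximum and "percentile/ median/ 75"th percentile. Both are repeated for three responder subgroups and for the four further definitions in Appendix 14.2. Total duration, in SAP 10.2.2, "will be analyzed in the similar way as duration of platelet response".

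SAP 4.4 has two censoring rules. "Patients who drop out of the study by the time of database lock while still maintaining a platelet response will be censored" at the last platelet measurement, and a patient still on study and in response "will be censored as of the time of the last platelet measurement prior to the time of database lock".

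The value 0 goes to "Patients who drop out of the study before achieving a platelet response". SAP 4.4 does not say whether that 0 is an event or a censored time. SAP 3.5 says such patients are censored and attributes this to the protocol, but Protocol 10.4.2 only assigns the 0. Protocol 10.4.2 plans Kaplan-Meier alone, and SAP 3.5 does not list the plain summary among its changes.

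**The concern.** A patient censored while in response contributes only a lower bound on duration. That value is recorded, so it counts as non-missing, and no rule excludes, flags or adjusts it. The plain rows then describe response time cut short by dropout or lock, under the name of response duration. The report would carry two medians for one secondary endpoint, with nothing to say why they differ. Long responders are the most affected, and they are the patients a study of up to five years exists to describe.

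The handling of 0 adds to this. If zeros are censored at time 0, they leave the Kaplan-Meier estimate but stay in the plain table, so the two medians describe different patients. Protocol 7.3 also lets a nonresponder stay on treatment "unless tangible clinical benefit from the use of fostamatinib is evident" and the Sponsor agrees. Such a patient who is still on study at lock, never having reached the threshold, has no assigned value at all.

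**Working it through.** **Inputs.** The documents give no expected duration, event count or censoring rate for this endpoint, so there is no planned figure to reproduce. The censoring rules come from SAP 4.4 and the 60-month ceiling from the five-year maximum in SAP 3.1. Everything else is assumed: exponential durations with true median m, lock uniform over 24 to 60 months after first response, and dropout while in response of p = 5% to 15% a year.

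**Direction.** Kaplan-Meier moves a censored patient's weight to later times; the plain summary leaves it at the censoring time. On the same patients the plain curve therefore cannot lie above the Kaplan-Meier curve. In 2,000 simulated samples the plain median never exceeded the Kaplan-Meier median and equalled it in 103.

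**Size, responders only.** Let λ = ln 2 / m and δ = −ln(1 − p)/12 per month. The observed time exceeds t with probability S(t) = exp(−(λ+δ)t) up to 24 months, multiplied by (60 − t)/36 after that. If the plain median is below 24 months it equals ln 2/(λ+δ).

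| True median m | Dropout | Calculation | Plain median |
|---|---|---|---|
| 24 | 5% | 0.6931/(0.02888 + 0.00427) | 20.9 |
| 24 | 15% | 0.6931/(0.02888 + 0.01354) | 16.3 |
| 36 | 5% | exp(−0.02353t)(60 − t)/36 = 0.5 | 26.5 |
| 36 | 15% | 0.6931/(0.01925 + 0.01354) | 21.1 |

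Reading 15% as a hazard of 0.15 a year changes the last row to 0.6931/(0.01925 + 0.0125) = 21.8. The plain mean is the area under S(t). It is 19.2 to 22.2 months against a true 24/ln 2 = 34.6, and about 22 to 26 against 36/ln 2 = 51.9. With m = 6 the plain median is 5.4 to 5.8. With no dropout and m = 24 it is exactly 24.0, but the mean is still about 24 against 34.6.

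**Version 1 responders.** Membership requires 12 months of maintained response. Take a further exponential median of 36 months after month 12 (true median 48), with no censoring before month 12. At 5% dropout the plain median is 31.5, since exp(−0.02353 × 19.5) × 28.5/36 = 0.50. At 15% it is 28.8, since exp(−0.0328 × 16.8) × 31.2/36 = 0.50.

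**Whole Treated Population.** Suppose a share z has the value 0, counted as an event, and responders have m = 24. The plain median solves (1 − z)S(t) = 0.5; for Kaplan-Meier, set δ = 0 and ignore lock.
- z = 30%: ln 1.4 = 0.3365. Plain 0.3365/0.03315 = 10.1 to 0.3365/0.04242 = 7.9; Kaplan-Meier 0.3365/0.02888 = 11.7.
- z = 45%: ln 1.1 = 0.0953. Plain 2.9 to 2.2; Kaplan-Meier 3.3.
- z above 50%: both are 0.

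The mean stays well short. At z = 30% it is 0.7 × 19.2 = 13.4 to 0.7 × 22.2 = 15.5, against 0.7 × 34.6 = 24.2.

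**Status of the zeros.** At z = 30%, Kaplan-Meier targets 11.7 months with zeros as events but 24 with zeros censored at time 0, because censored zeros leave the risk set before any loss is counted. That difference of 12.3 months exceeds the plain-versus-Kaplan-Meier gap in the same setting.

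**The case against.** The right method is already the named one, with its confidence interval. The plain rows are supplementary, carry no test, and could be made harmless by a label. That stands, and it limits this to a reporting and interpretation problem.

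The SAP never says in words that censored values are treated as complete; this is inferred from the count of non-missing durations and the absence of a rule. Limiting the table to observed losses of response does not rescue it. With m = 24, lock at 24 to 60 months and dropout of 20% a year, that reading gives a median of 11.6 months, against 14.6 with censored values included.

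A reader might infer that the plain median is always too short. It is not: it equals the Kaplan-Meier median when nobody is censored before that point, or when more than half the patients have 0 counted as an event. A reader might also apply the responder figures to the main table. They do not describe it, because the zeros of never-responders pull both medians down and together.

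Nor does every nonresponder kept on treatment lose a value. One who later drops out does receive 0 under SAP 4.4; only those still on study at lock are left out. Their number is not given, and retention is an exception that needs Sponsor agreement. The protocol's example of benefit includes reaching 30,000/µL, which already meets the threshold of the third and fourth definitions in Appendix 14.2.

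Finally, Kaplan-Meier is not a simple cure for total duration. A patient who accumulates response time slowly is censored at a smaller total, so censoring on that scale depends on the outcome.

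**Conclusion.** The point holds as a reporting flaw in SAP 10.2.1. The plain mean is too short whenever anyone is censored. The plain quartiles, including the median, are shorter than or equal to their Kaplan-Meier counterparts. Under the stated assumptions the median shortfall among responders is about 3 to 8 months at a true 24 (24 − 20.9 to 24 − 16.3) and about 10 to 15 months at a true 36 (36 − 26.5 to 36 − 21.1). At a true 6 it is about 0.6 month or less. In the whole Treated Population, with responders at 24 months, it is about 1.6 to 3.8 months with 30% zeros and about 1 month or less with 45%. All of these rest on assumed rates; only the direction follows from the documents.

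One might go further and say that the duration endpoint itself is invalid. The documents do not support that: Kaplan-Meier remains the stated analysis. It does, however, need a settled rule for the zeros, because SAP 3.5 and SAP 4.4 can be read to give different estimates.

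**What to change.** 1. In SAP 10.2.1, including its use of the Appendix 14.2 definitions, replace the plain summary with Kaplan-Meier 25th, 50th and 75th percentiles with confidence intervals and the numbers of events and censored patients. A restricted mean to a stated horizon is optional. If the plain rows are kept, title them *observed time in response, censored values included*, not response duration.
2. In SAP 10.2.2, label the plain summary as observed total time in response. Do not mandate Kaplan-Meier quartiles for the summed durations.
3. Reconcile SAP 3.5 with SAP 4.4 and Appendix 14.2. Count 0 as an event at time 0 in the Treated Population analysis. Assign it to every treated patient who never reaches the threshold of the definition in use, including those still on study at database lock.
4. List the resulting differences from Protocol 10.4.2 in SAP 3.5.

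The cost is SAP wording and table shells; no new data are needed. The downside is that some planned descriptive rows disappear or are relabelled.
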